### **19.2. Ethical principles**

This trial complies with the principles laid down by the 18th World Medical Assembly (Helsinki, 1964) and all applicable amendments laid down by the 18th World Medical Assemblies, and the ICH guidelines for Good Clinical Practice.

### **19.3. Laws and regulations**

This Clinical Trial will be conducted in compliance with the International and National laws and regulations of the country(ies) in which this Clinical Trial is performed, as well as any applicable guidelines.

### **19.4 Research Ethics Board/Institutional Review Board/Independent Ethics Committee (REB/IRB/IEC)**

The Investigator must submit this protocol to the appropriate Ethics Committee (REB/IRB/IEC), and is required to forward to the Sponsor a copy of the written and dated approval signed by the Chairperson of such committee (REB/IRB/IEC).

## **20. STATISTICAL METHODOLOGY**

A total of approximately 95 subjects will be randomized to treatment with ACP-01 or placebo using a 2:1 randomization scheme, respectively, stratified by site. Study will be continued until all subjects treated with the IMP are followed-up for 52 weeks.

One futility analysis for potentially stopping enrolment into the study will be performed when approximately 42 subjects have completed at least 26 weeks of follow-up but no more than 52 weeks from IMP administration or experienced before that time point the study event.

### **20.1. Randomization Procedure**

After a subject meets the eligibility criteria, he/she will be randomized to one of the two treatment groups, based on a randomization procedure employing a 2:1 assignment ratio, i.e., treatment with ACP-01 or placebo, respectively, using permuted blocks stratified by centers. #

### **20.2. Interim Analysis**

Interim analyses will be conducted according to the Lan & Demets (1983) maximum information group sequential test, in which the Type I error spent at each analysis  $k$  is a function of the observed information level, using the error spending function family

$$f(t) = \min\{\alpha_{tp}, \alpha\},$$

where  $t$  = fraction of the maximum anticipated information obtained at the time of analysis  $k$ . To maintain the blind, interim analyses will be conducted by an independent party without unblinding either the Sponsor or Investigators to the treatment assignments.

### **20.3. Significance Level**

The overall significance level for this study will be 5% using two-tailed tests. The study will have one primary endpoint and 2 secondary end-points ordered in a hierarchy, and analyses will utilize the gatekeeping approach to maintain the experiment-wise type-I error of 5%. The order of the hierarchy of the secondary endpoints testing following the primary end-point testing is as follows:

- Change from Baseline in VAS pain score
- Change from Baseline in Ulcer Size

### **20.4. Sample Size**

Sample size calculations were performed under the following assumptions:

- The primary study endpoint is the earlier time from treatment with study IMP to either de-novo gangrene, or doubling of wound size, or major amputation, or death.
- Randomization will allocate subjects to autologous ACPs or placebo using a 2:1 assignment ratio, respectively, stratified by site.
- The expected median time to study event as defined by the primary efficacy endpoint, assuming exponentially distributed time to event, is 3 months for placebo-treated subjects and 7 months for the ACP-treated arm.

- The anticipated monthly randomization and study IMP administration rate is 6 subjects per month.
- The minimal follow-up period of a subject will be 26 weeks if the primary endpoint is not reached, and the maximal follow-up period will be 52 weeks.
- Final analysis, under these assumptions is planned to be conducted at approximately at 22 months from first subject IMP treatment including a total of 95 subjects.
- As the effect of the early futility analysis is marginal, the final analysis will use a two-sided alpha level of 0.05

Under the above assumptions, a total of 95 subjects treated with the study IMP will provide 94% power to detect a statistically significant result at a two-sided alpha level as specified above.

#### Sample Size Re-estimation

Periodic, blinded review of the overall, pooled event rate will be conducted using the method of Gould and Shih(1992). If the observed overall event rate is lower than anticipated at study initiation, this procedure will allow for adjusting the sample size without altering the significance level. Consistent with FDA guidance (2018), Adaptive Designs for Clinical Trials of Drugs and Biologics Guidance for Industry, such sample size adjustments require no adjustment of Type I error:

In general, adequately prespecified adaptations based on non-comparative data have a negligible effect on the Type I error probability.

#### **20.5. Analysis Sets**

- Intent-to-Treat (ITT) Analysis Set: The intent to treat (ITT) analysis set will consist of all subjects who have been randomized to the study. In accordance with the ITT principle, all subjects randomized will be kept in their originally assigned treatment group. This analysis set will serve as the primary analysis set for efficacy inference.
- Modified Intent-to-Treat (mITT) Analysis Set: The mITT analysis set is a subset of the ITT analysis set. This set will consist of data from all subjects who have been randomized to the study and administered the IMP and had at least one treatment visit post IMP administration.
- Per-Protocol (PP) Analysis Set: The per protocol (PP) analysis set is a subset of the mITT analysis set and will consist of all subjects with no major protocol violations as will be defined in a more detailed Statistical Analysis Plan (SAP) to be written prior to revealing of the blind and having follow up assessments available.

- Safety (ST) Analysis Set: The safety analysis set (ST) will consist of all subjects who have been randomized and received the Study IMP. This analysis set will be used as the primary set for safety inference.

## **20.6. Demographics and Baseline Characteristics**

Demographics and baseline data will be described for the ITT analysis set. Subject demographics and baseline characteristics, including underlying disease history, medical history and prior medications will be compared between the study groups to assess baseline comparability. Continuous variables (e.g., subject age, weight, height, and body mass index (BMI)) will be summarized using descriptive statistics (number [n], mean, standard deviation, and standard error, median, minimum, and maximum) Categorical variables will be summarized using subject counts and percentages. Categories for missing data will be presented if necessary.

## **20.7. Efficacy Assessment**

The following trial end-points will be calculated and statistically analyzed for the ITT cohort which will serve as the primary analysis set for efficacy inference.

### **20.7.1. Primary End-Point and Principal Analysis**

The primary efficacy end-point for this study is the earlier time from treatment with IMP to either de-novo gangrene, or doubling of wound size, or major amputation, or death. The time to the primary end-point will be presented by Kaplan-Meier curves stratified by treatment group.

The time from day of treatment with the IMP to the earlier time of either de-novo gangrene, or doubling of wound size, or major amputation, or death will be right censored by the subject's last follow-up date in the study.

The primary analysis for the between study groups comparison will be conducted utilizing the baseline adjusted Cox's proportional hazards (PH) model (SAS® PROC PHREG). In addition to treatment group and study site, baseline prognostic factors as will be defined in a more detailed SAP written prior to revealing of the blind will be included as covariates in the model.

The adequacy of the proportional hazards (PH) assumption will be confirmed by including a time dependent covariate for the active treatment group (as dummy variable) by log (time) interaction in the primary analysis model and testing it using 5% significance level. In case the PH assumption will be rejected the log rank test (SAS® PROC LIFTEST) will be used for statistical inference. A detailed sensitivity analysis of the principal analysis of the primary endpoint will be provided in a more detailed SAP to be sent to the Division prior to revealing of the blind and conduct of the pre-defined futility analysis.

### 20.7.2. Key Secondary Endpoint Analyses

#### 20.7.2.a. Change from Baseline in VAS pain score

The change from baseline in VAS pain score is defined at the difference between the Last Observed Value (LOV) of an individual subject subtracted from the last measurements taken prior to study IMP administration. Subjects who early terminated from the study or met the study event will be imputed a value according to the worst-case scenario; the worst recorded measurement of change of the entier study population.

The model baseline adjusted Least Squares Means (LSM) of the change from baseline to LOV of this endpoint will be compared the two study groups by applying an ANCOVA model (SAS® MIXED procedure). The model will include treatment group, study site and baseline pain measurement.

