#### 7.1.1. Visit 1: Day –30 to -7

- 1) Evaluation according to the inclusion/exclusion criteria to determine eligibility.
- 2) Obtain and record medical history including current clinical condition, chronic disabilities and current medication/therapy, obtain and record demographical data, review angiography or color flow duplex ultrasound imaging results.
- 3) Assessment of pain on a visual analogue scale (VAS).
- 4) Type and dose of analgesic drug taken by subject.
- 5) Physical examination including Rutherford Assessment.
- 6) Measurement of blood pressure, heart rate, ECG, and temperature (to reduce the likelihood of infection prior to administration of the IMP).
- 7) Leg assessment, including skin color, swelling, limb temperature, presence of ulcers or gangrene, bilaterally.
- 8) Measurement of resting ankle blood pressure using an appropriate adult cuff, bilaterally
- 9) Measurement of toe blood pressure using an appropriate cuff, bilaterally.
- 10) Assessment of leg ulcers, measurement of ulcer size and ulcer photography, bilaterally.
- 11) Vascular quality of life (QoL) questionnaire (Morgan et al., 2008).
- 12) Blood tests:
  - *Hematology:* RBC; Hemoglobin; Hematocrit; WBC; Neutrophils; Lymphocytes; Monocytes; Platelet count, PT (or INR), and aPTT

- *Blood Chemistry:* Blood glucose; Blood urea nitrogen (BUN); Serum creatinine; C-reactive protein; Serum chloride; Serum potassium; Serum sodium; Serum magnesium; Serum albumin; Total serum protein; SGOT/AST; SGPT/ALT; Alkaline phosphatase; Total bilirubin, Creatine phosphokinase (CPK), HbA1c.
- Pregnancy test (serum Beta-hCG), if female of childbearing age.
- Screening for severe contagious infections: HIV-1, HIV-2, HTLV-1, HTLV-2, HBV, HCV.

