#### 7.2. Visit 3: Treatment (Day 0)

Preparation of the subject for the treatment procedure will be initiated upon communication by Hemostemix's representative of the estimated date of the investigational product delivery.

If the batch is not released due to failure to meet release specifications, the subject will undergo a repeat Visit 2 within 21 days of the first Visit 2.

If the batch of IMP produced from the second blood also fails to meet specified release criteria, the subject will be withdrawn from the study.

The following clinical assessments will be performed just prior to the administration of the IMP.

- Physical examination, including Rutherford Assessment.
- Standard preoperative monitoring of heart rate, blood pressure, ECG, and body temperature.
- Assessment of ulcers including measurement of area in  $\text{cm}^2$  based on photography of lesions.

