3.3.3. Secondary efficacy endpoints

The change from baseline in VAS pain score in the treated limb is defined as the difference between the Last Observed Value (LOV) of an individual subject subtracted from the last measurement taken prior to study IMP administration. Subjects who early terminated from the study or met the study event will be imputed a value according to the worst-case scenario; the worst recorded measurement of change of the entire study population.

The change from baseline in Ulcer Size (cm^2) in the treated limb is defined as the difference between the Last Observed Value (LOV) of an individual subject subtracted from the last measurement taken prior to study IMP administration. Subjects who early terminated from the study or met the study event will be imputed a value according to the worst-case scenario; the worst recorded measurement of change of the entire study population. In addition, Ulcer Size at baseline will be treated as zero if Ulcer is not present.

In order to control the overall Type I error rate for the primary and secondary hypotheses, the following sequential testing procedure will be implemented in the following order:

- Change from Baseline in VAS pain score in the treated limb
- Change from Baseline in Ulcer Size in the treated limb

The model baseline adjusted Least Squares Means (LSM) of the change from baseline to LOV of each of key secondary endpoints will be compared between the two study groups by applying an ANCOVA model. The model will include treatment group, study site and baseline pain measurement or baseline ulcer size measurement.

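### Pain VAS, the first key secondary endpoint, has no scheduled measurement between screening Visit 1 and injection, so its baseline is 7 to 30 days old, whereas ulcer size is re-measured on Day 0

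*Protocol*

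**What the plan says.** **Endpoint and rank.** Protocol 20.3 puts change in pain VAS first of the two gated secondary endpoints, ahead of ulcer size. SAP 3.3.3 keeps that order.

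**Baseline.** Protocol 20.7.2.a takes the last observed value "subtracted from the last measurements taken prior to study IMP administration". SAP 3.3.3 restricts the endpoint to the treated limb and repeats the rule: "subtracted from the last measurement taken prior to study IMP administration". The ANCOVA in both documents includes treatment group, site and the baseline pain score.

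**When VAS is taken.** Section 7.1.1, headed "Visit 1: Day –30 to -7", lists VAS. Section 7.1.2 (Visit 2, Day -7 ± 1) lists blood tests, the blood draw and shipping. Section 7.2 introduces its Day 0 list with "The following clinical assessments will be performed just prior to the administration of the IMP" and names a physical examination with Rutherford grade, vital signs with ECG, and ulcer area. VAS is not on it. The Section 14 table agrees: VAS is marked at Visit 1, blank at Visits 2 and 3, and marked again from Visit 4. Ulcer size is marked at Visit 3.

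**Failed batch.** Section 7.2 states that "the subject will undergo a repeat Visit 2 within 21 days of the first Visit 2". It does not say whether Visit 1, or any measure taken there, is repeated.

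**The concern.** The baseline rule reads as if it captures the subject's state at injection. For ulcer size it does. For pain the schedule makes it a screening score, so the change score combines any movement between screening and injection with movement after injection. The mean change in each arm then does not describe change since treatment. The covariate also sits further from the outcome than it needs to, which tends to weaken the adjustment.

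The protocol itself allows for change in that interval: Section 7.2.1 lists marked clinical deterioration among the reasons not to inject on the planned day. Because pain is tested first, any precision lost there also affects whether ulcer size can be tested at all.

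The repeat-draw rule adds a second problem, since the documents leave open how old the Visit 1 score may become after a failed batch.

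**Working it through.** **Plan's own figure.** There is none for this endpoint: no power, standard deviation or correlation is given for VAS. The 94% power in protocol 20.4 concerns the primary endpoint.

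**1. Age of the baseline, normal schedule.** Visit 1 is Day -30 to -7 and nothing later is scheduled before injection, so the age is 7 to 30 days. With a pre-dose VAS at Visit 3 it would be 0.

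**2. Age after a repeat draw.** Inputs are Visit 1 at Day -30 (7.1.1), Visit 2 at Day -7 ± 1 (7.1.2) and a repeat within 21 days (7.2).
- Visit 1 to first Visit 2: 30 − 7 = 23 days.
- First to repeat Visit 2: up to 21 days.
- Repeat Visit 2 to Day 0: 7 days.
- Sum: 23 + 21 + 7 = 51 days. With the ±1-day windows: (22 to 24) + 21 + (6 to 8) = 49 to 53 days.

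This holds only if Visit 1 is not repeated and the Day -30 limit is not re-applied to the actual Day 0. If the limit is re-applied, the maximum stays 30 days. A repeat at the full 21 days would then leave only 30 − 21 − 7 = 2 days between Visit 1 and the first Visit 2. The two rules cannot both be used to their limits.

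**3. How precision might respond (assumptions, not plan figures).** With baseline-to-outcome correlation ρ, ANCOVA residual variance is proportional to 1 − ρ². Suppose ρ = 0.6 for a same-day baseline and that correlation decays exponentially with lag, so that ρ(new) = 0.6^(new lag/old lag).

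| Day 0 to last value | Baseline age | ρ | 1 − ρ² | Ratio to 0.64 |
|---|---|---|---|---|
| 365 days | 30 days | 0.6^(395/365) = 0.575 | 0.669 | 1.045 |
| 365 days | 51 days | 0.6^(416/365) = 0.559 | 0.688 | 1.075 |
| 182 days | 30 days | 0.6^(212/182) = 0.552 | 0.696 | 1.09 |
| 182 days | 51 days | 0.6^(233/182) = 0.520 | 0.730 | 1.14 |

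The increase in variance is 4.5% to 14% under these assumptions. A steeper fall would cost more: to ρ = 0.5, 0.75/0.64 = 1.17; to ρ = 0.4, 0.84/0.64 = 1.31. But a drop from 0.6 to 0.4 in 30 days, continued at the same rate, multiplies the correlation by (0.4/0.6)^(365/30), less than 0.01, over a year. That does not fit a correlation of 0.6 at 12 months.

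**4. How many subjects this touches.** Both documents give subjects with an event or early termination the worst recorded change. Take the design assumptions: medians of 3 and 7 months, 95 subjects accrued at 6 per month, analysis at 22 months, a 12-month cap and 2:1 allocation. The event probabilities are then 91.2% (placebo) and 65.6% (ACP-01). Expected events are 31.67 × 0.912 + 63.33 × 0.656 = 70.4, and 70.4/95 = 74%. SAP 1.3 requires at least 51 events from 65 subjects, 51/65 = 78%. For those subjects the change score is a common constant, and their own baseline enters only as a covariate. The ratios in step 3 therefore do not carry over to the whole sample.

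**The case against.** **A screening baseline is a stated choice.** Section 7.1 says the screening examinations supply baseline values, and the amendment log gives the reason for the Day 0 ulcer re-measurement as confirming eligibility. This stands as an account of how the gap arose. It does not make a screening score equivalent to a Day 0 score.

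**No bias.** Both arms follow the same schedule and the ANCOVA adjusts for baseline. This stands. A reader might infer that an old baseline distorts the treatment comparison, but nothing in the documents shows that. They also do not say whether batches can fail for placebo subjects, which is one reason to report the interval by arm.

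**51 days is not the rule.** A reader might take 51 days as the permitted age. It exceeds the printed Day -30 limit and depends on two things the documents leave unstated. No batch-failure rate is given, so the number affected is unknown.

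**Disease pace does not measure pain instability.** A reader might apply the assumed 3-month placebo median and conclude that pain cannot be stable: 1 − 2^(−30/91.3) = 20% with an event in 30 days, and 32% in 51 days. That median is for gangrene, wound doubling, amputation or death counted from dosing, not for pain. Subjects who deteriorate before injection may also be withheld under 7.2.1. At the pooled interim median of 241 days in SAP 1.3, with exponential times, the figures are 1 − 2^(−30/241) = 8% and 1 − 2^(−51/241) = 14%.

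**A large precision loss is not shown.** A variance increase of 17% to 31% needs correlations that the documents do not give, and it ignores both the long lag to the last observed value and the worst-case imputation.

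**It is late.** SAP 1.3 reports 65 subjects treated by the April 2020 export and plans on 65 evaluable, with about 8 more possible. A new Day 0 VAS would reach few or none of them, so an analysis remedy is needed as well.

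**Conclusion.** The gap is real and can be read directly from the visit lists and the schedule table. On the normal schedule the pain baseline is 7 to 30 days old, while the other key secondary endpoint is re-measured on Day 0. After a repeat draw the age is unresolved: at most 30 days if the Day -30 limit is re-applied, and about 51 days in the worst case if it is not and Visit 1 is not repeated.

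The consequence is some loss of precision and a change score that includes pre-treatment drift. It is not a demonstrated between-arm bias. The documents give no VAS standard deviation or correlation, so the loss cannot be computed. It is probably modest, because the last observed value can be up to a year after dosing and most subjects are expected to carry the imputed worst-case change. The 4.5% to 14% range is an illustration that rests on an assumed correlation of 0.6 and exponential decay. This is a cheap improvement, not a flaw that threatens the trial's conclusion.

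**What to change.** - **Subjects not yet dosed:** add VAS to the Visit 3 pre-dose list in 7.2 and to the Visit 3 column of Section 14, recorded before any analgesia or sedation for the injections. Name it as the baseline in protocol 20.7.2.a and SAP 3.3.3.
- **Subjects already treated:** state in SAP 3.3.3 that baseline is the Visit 1 score, report the Visit 1-to-dosing interval by arm, and add a sensitivity analysis with that interval as a covariate.
- **Repeat draw:** reconcile the Visit 1 window (7.1.1, Section 14) with the repeat Visit 2 rule (7.2), and state whether Visit 1 measures are repeated.

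**Cost:** a short assessment at a visit the subject already attends, one entry in the table, one CRF item, and one extra model and table in the analysis. If the change is made mid-study, baseline is measured at two different time points. The interval report and the sensitivity analysis make that visible.

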#### 20.7.2.b. Change from Baseline in Ulcer Size

The change from baseline in Ulcer Size ( $\text{cm}^2$ ) is defined at the difference between the Last Observed Value (LOV) of an individual subject subtracted from the last measurements taken prior to study IMP administration. Subjects who early terminated from the study or met the study event will be imputed a value according to the worst-case scenario; the worst recorded measurement of change of the entier study population.

The model baseline adjusted Least Squares Means (LSM) of the change from baseline to LOV of this endpoint will be compared the two study groups by applying an ANCOVA model (SAS® MIXED procedure). The model will include treatment group, study site baseline ulcer size measurement.

The model adjusted Least Squares Means (LSM) of the change from baseline to LOV of this endpoint will be compared by applying an ANCOVA model (SAS® MIXED procedure). The model will include treatment group, study site and baseline toe pressure measurement.

### 20.7.3. Exploratory Outcome Measures

Additional exploratory endpoints as described below will be analyzed for further exploration of the ACP treatment effect with no multiplicity adjustment. Assessments will be done for Study Week 13 and Week 26 and will be described in a more detailed SAP to be sent to the Division prior to revealing of the blind and conduct of the pre-defined futility analysis. The pre-defined exploratory outcome measures are:

- Change from baseline in the dose and quantity of analgesic drugs used by the subject.
- Change from Baseline in Quality of Life
- Change from Baseline in Ankle Pressure
- Change from Baseline in Toe Pressure

- Proportion of subjects with an improvement in VAS pain score
- Change from baseline in Ulcer Size.

